### 5.6.1. Primary analyses vs. PNCR

For the cohort of patients  $\geq$  6 months and  $<$  24 months of age, patient-level data from a cohort of 51 patients drawn from the PNCR Network natural history study of SMA will serve as a “population-matched” control cohort. This comparison cohort encompasses all 51 patients enrolled in the PNCR study who met the criteria of having SMA Types 2 or 3, 3 copies of *SMN2* and symptom onset before 12 months of age and had at least one visit at or before 36 months of age. Of this cohort, 7/51 (14%) of the natural history cohort attained the ability to stand alone (defined as achieving a score of 2 on item #19 of the HFMSE). 5/51 (10%) attained the ability to walk alone (defined as achieving a score of 2 on item #20 of the HFMSE).

For the cohort of patients between 24 and  $<$  60 months of age, patient-level data from a cohort of 15 patients drawn from the PNCR Network natural history study of SMA will serve as a “population-matched” control cohort for the primary analysis. This comparison cohort encompasses all 15 patients enrolled in the PNCR study who met the criteria of having SMA Types 2 or 3, 3 copies of *SMN2*, symptom onset before 12 months of age, diagnosis before 24 months of age and unable to stand or walk at enrollment (baseline visit) and who received a HFMSE evaluation between 24 and 60 months of age (“baseline”), and a follow-up evaluation

(HFMS or HFMSE) performed between 12 and 14 months following that baseline evaluation. It is stated in the protocol that among the patients in this cohort, a mean change of -1.33 points (Standard deviation=4.32) was seen in HFMS. However, the primary endpoint for this cohort is HFMSE, not HFMS. As such, the comparison to PNCR will utilize HFMSE. Among patients in this PNCR cohort, a mean change of -1.13 points (Standard deviation=4.90) was seen in HFMSE, in line with other publications describing disease progression in SMA type 2 and 3 patients (Kaufman et al 2012, Mercuri et al 2016). From this point forward, this PNCR comparator group of 15 patients will be referred to as the “Primary PNCR” group.

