#### **14.6.2.1. Primary Efficacy Endpoint: patients $\geq 6$ months and $< 24$ months at time of dosing**

The primary efficacy endpoint is the proportion of patients  $\geq 6$  months and  $< 24$  months at time of dosing that achieve the ability to stand alone, without support for at least 3 seconds (Bayley Scales of Infant and Toddler Motor Development – Gross Motor subset item # 40) up to the 12-month study visit. A Responder for the primary endpoint of standing alone will be defined as per the Bayley Scales of Infant and Toddler Motor Development – Gross Motor subset item #40 – the child stands alone for at least 3 seconds after you release his or her hands.

The proportion of patients  $\geq 6$  months and  $< 24$  months of age at time of dosing achieving the ability to stand without support up to the 12-month study visit will be compared between AVXS-101 and natural history control groups using a two-sample 2-sided superiority Fisher exact test. A 95% exact conditional confidence interval for the difference in response rates will be computed.

The primary analyses will be based on the Full Analysis Set for patients  $\geq 6$  months and  $< 24$  months of age at the time of dosing.

A sensitivity analysis will be conducted by repeating each primary efficacy analysis on the Efficacy Completers Analysis Set for patients  $\geq 6$  months and  $< 24$  months of age at the time of dosing.

A supportive analysis will be conducted by repeating the analysis of the primary efficacy endpoint for patients  $\geq 6$  months and  $< 24$  months of age considering data through the 15-month visit.

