## 4. ENDPOINTS

### 4.1. Primary Efficacy Endpoints

Primary efficacy endpoints are assessed independently for each age group and for each dose separately. As detailed in Section 3.4.1 of this SAP, Dose A and Dose C will each be summarized descriptively and will not be compared to the historical data of the PNCR network. Assessment of developmental milestones will be determined by the clinical evaluator (CE) at the investigative sites. The primary source for developmental milestone data will be based on documented video evidence captured by site CE or patient families that is reviewed and concurred by an independent central reviewer.

- Patients  $\geq$  6 months and  $<$  24 months at time of dosing:

The primary efficacy endpoint is the proportion of treated patients who achieve the ability to stand alone (Bayley-III – Gross Motor Subtest item # 40) at any post-treatment visit up to the 12-month study visit.

- Patients  $\geq$  24 months and  $<$  60 months at time of dosing:

The primary efficacy endpoint is the change from baseline in HFMSE in treated patients at the 12-month study visit.

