## 5.6. PNCR Population-Matched Control Population

A population-matched control cohort will be drawn from the PNCR Natural History dataset. The PNCR is a large natural history study developed from a cohort of 337 patients with any form of spinal muscular atrophy followed at 3 large, internationally recognized tertiary medical centers with significant expertise in the management of SMA (Harvard University/Boston Children's Hospital, Columbia University and the University of Pennsylvania/Children's Hospital of Philadelphia).

Previously identified patients with any form of SMA, of any age, followed in PNCR site clinics and newly diagnosed patients were enrolled. All eligible patients were offered participation. Study visits were scheduled at baseline and at 2, 4, 6, 9, and 12 months and every 6 months thereafter. The SMA standard of care guidelines published in 2007 were used as a basis for providing uniform care among the study sites.

For purposes of this study, sitting (for SMA-II) was defined as being able to sit independently for > 10 seconds, and walking alone was defined as having scored 2 points on item #20 of the HFMSE at any time. All patients with SMA type 2 or 3 who provided sufficient records and follow-up for evaluation and met the basic entry criteria for the two cohorts of the AVXS-101-CL-102 study (3 copies of *SMN2*, symptom onset before 12 months of age and baseline and follow-up visits within the age criteria for the study) were considered for possible inclusion in the natural history comparison dataset. The *SMN2* modifier mutation (c.859G>C) described by Prior and colleagues (Prior et al., 2009) was not assessed in the PNCR study cohort.

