**Table 3: Developmental Milestone Checklist**

Developmental Milestone- Bayley Scales Item Number	Performance Criteria
Head Control – Gross Motor Subtest Item #4	Child holds head erect for at least 3 seconds without support
Rolls from Back to Sides – Gross Motor Subtest Item #20	Child turns from back to both right and left sides
Sits Without Support – Gross Motor Subtest Item #26	Child sits alone without support for at least 30 seconds
Stands With Assistance - Gross Motor Subtest Item #33	Child supports own weight for at least 2 seconds
Crawls – Gross Motor Subtest Item #34	Child makes forward progress of at least 5 feet by crawling on hands and knees
Pulls to Stand – Gross Motor Subtest Item #35	Child raises self to standing position using chair or other convenient object for support
Walks With Assistance – Gross Motor Subtest Item #37	Child walks by making coordinated, alternated stepping movements
Stands Alone – Gross Motor Subtest Item #40	Child stands alone for at least 3 seconds after you release his or her hands
Walks Alone – Gross Motor Subtest Item #43	Child takes at least five steps independently, displaying coordination and balance

The primary efficacy endpoint for the patients  $\geq$  6 months and  $<$  24 months at time of dosing is the proportion of patients achieving the ability to stand alone. The ability to stand alone will be evaluated by the CE using the Bayley-III – Gross Motor Subtest # 40 at visits specified by the Schedule of Assessments. Patients who achieve standing alone at any post-procedure visit up to 12 months will be classified as responders. Otherwise, the patient will be classified as a non-responder.

The HFMSE was devised for use in children with SMA Type 2 and Type 3, age 24 months and above, to give objective information on motor ability and clinical progression. The HFMSE will be administered by a CE in accord with the Protocol Schedule of Assessments within 30 days of dosing and monthly through twelve (12) months for all patients  $\geq$  24 months of age. The primary efficacy endpoint for the patients  $\geq$  24 months and  $<$  60 months at time of dosing is the change from baseline in HFMSE. The change from baseline to the 12-month study visit will be calculated.

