### 8. EFFICACY

#### 8.1. Primary Efficacy Endpoints and Analysis

##### 8.1.1. Proportion of patients $\geq$ 6 months and $<$ 24 months at time of dosing that achieve the ability to stand alone at any post-baseline visit up to 12 months

The developmental milestone stands alone as assessed by Bayley-III Gross Motor Subtest #40 will be assessed at the scheduled visits in accord with the Schedule of Assessments for evaluating patient’s ability to stand alone. The developmental milestone achievement of each patient in the study is based on the video evidence reviewed and confirmed by an independent central reviewer, as specified in SAP Section 6.4.3. The proportion of patients  $\geq$  6 months and  $<$  24 months of age at time of dosing that achieve the developmental milestone at any post-baseline visit up to 12 months will be summarized overall and by dose.

The proportion of patients achieving the corresponding developmental milestone “stand unsupported” assessed using the HFMSE item #19 within 12 months in the historical dataset of PNCR network will also be included by the matched age group. PNCR patients with an HFMSE item #19 score of 2 at either the Baseline visit or at any post-Baseline visit within 12 months of Baseline will be considered to have achieved the milestone. The HFMSE will not be started until patients reach 24 months of age; however, the Bayley-III will be assessed at Screening and all study visits as indicated in the Schedule of Assessments. An additional summary will be produced to present the proportion of patients achieving the developmental milestone at each visit; this will be summarized overall and by dose.

The corresponding p-value from Fisher’s exact test will be computed for the comparison between AVXS-101 Dose B and PNCR data and this is the primary analysis for this endpoint. The summary and statistical analysis will be conducted using the ITT Set and will be repeated using the PP Set as a sensitivity analysis. The difference of the proportions between AVXS-101 and PNCR will be summarized and the exact 95% CIs will be provided accordingly.

As a supporting analysis to the primary analysis, the time to achieving ability to stand alone will be summarized for patients overall and by dose in the ITT Set. The study day will be used as the

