18 Supported standing	Can you stand using one hand for support for a count of 3?	Can stand using one hand support for a count of 3	Able to stand with minimal trunk support (not hip) for a count of 3	Can stand with hand support but needs knee/hip support in addition for a count of 3  Or unable			
19 Stand unsupported	Can you stand without holding onto anything for a count of 3?	Can stand independently for the more than a count of 3	Stands independently for a count of 3	Stands only momentarily (less than a count of 3)  Or unable			
20 Stepping	Can you walk without using any help or aids? Show me	Able to take more than 4 steps unaided	Able to take 2 – 4 steps unaided	Unable			
SCORE		No of 2's =	No of 1's =	No of 0's =	TOTAL = /40		
Comments							

PNCR		Expanded Hammersmith Functional Motor Scale for SMA (HFMSE)			add-on module			07/03/09
Test	Instruction	2	1	0	L B C	S	Comments S = score	
21 Right hip flexion in supine	Can you bring your right knee to your chest?	Full hip flexion achieved	Initiates right hip and knee flexion (more than 10% of available range of motion)	Unable				
22 Left hip flexion in supine	Can you bring your left knee to your chest?	Full hip flexion achieved	Initiates left hip and knee flexion (more than 10% of available range of motion)	Unable				
23 High kneeling to right half knee	Can you bring your left leg up so that your foot is flat on the ground without using your arms and hold for a count of 10?	Arms used for transition, maintains arms free in half knee for a count of 10	Maintains half knee with arm support for a count of 10	Unable				
24 High kneeling to left half knee	Can you bring your right leg up so that your foot is flat on the ground without using your arms and hold for a count of 10?	Arms used for transition, maintains arms free in half knee for a count of 10	Maintains half knee with arm support for a count of 10	Unable				
25 High kneeling to stand leading with left leg	Can you stand up from this position starting with your left leg without using your hands? May need demonstration	Able with arms free	Able to shift weight off both knees (with or without arm support)	Unable				
26 High kneeling to stand leading with right leg	Can you stand up from this position starting with your right leg without using your hands? May need demonstration	Able with arms free	Able to shift weight off both knees (with or without arm support)	Unable				

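### If a count of 3 is about 3 seconds, PNCR controls face a stricter standing-alone threshold than treated children, and no visible planned analysis tests the effect

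*SAP*

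**What the plan says.** **Treated children.** Protocol 14.6.2.1 defines a responder by Bayley #40: "the child stands alone for at least 3 seconds after you release his or her hands". SAP Table 3 has the same criterion: "Child stands alone for at least 3 seconds after you release his or her hands". Any visit up to Month 12 counts. SAP 4.1 makes the primary source "documented video evidence captured by site CE or patient families that is reviewed and concurred by an independent central reviewer".

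**PNCR controls.** SAP 8.1.1 counts a control as having the milestone with an HFMSE item 19 "score of 2 at either the Baseline visit or at any post-Baseline visit within 12 months of Baseline". The form in SAP Appendix 19.1 describes score 2 as "Can stand independently for the more than a count of 3" and score 1 as "Stands independently for a count of 3". SAP 5.6.1 reports that 7/51 (14%) of the controls "attained the ability to stand alone (defined as achieving a score of 2 on item #19 of the HFMSE"), with no time limit stated.

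**Planned analyses.** SAP 8.1.1 and 8.4 show a Fisher test on the ITT Set, repeats on the PP Set and possibly the ECAS, Kaplan-Meier and Cox analyses, and optional COVID-19 window analyses. All keep score 2 for controls. The Sensitivity PNCR group is used only for ages 24 to <60 months.

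**The concern.** The treated rule includes a stand of exactly 3 seconds. The control rule excludes a stand of exactly a count of 3. If the two units are about equal, the nearest counterpart of Bayley #40 on the item 19 form is a score of 1 or 2, and requiring 2 sets the bar one category higher for controls.

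Walking does not have this problem. Item 20 score 2 needs more than 4 steps and Bayley #43 needs at least five, which is the same threshold in whole steps. The score-2 convention therefore fits the secondary endpoint but not clearly the primary one, and the SAP gives no reason.

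This is a non-randomised primary comparison. If some controls scored 1 at best, the risk difference, p-value and hazard ratio combine a treatment effect with a difference in definition, and the planned output would not show how much of each.

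**Working it through.** **Inputs.** Dose B n=12, expected response 85%, two-sided Fisher exact test at 0.05 (SAP 3.7). Controls 7/51 (SAP 5.6.1). Two quantities are not in the documents: k, the number of controls whose best item 19 score is 1, and the score-2 count within 12 months of Baseline that the test actually uses. Both are shown as ranges.

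**The plan's own figures.** 7/51 = 13.7%, which rounds to the stated 14%. Exact power is the sum, over treated counts a from Binomial(12, 0.85) and control counts b from Binomial(51, 7/51), of the probability of every pair with Fisher p ≤ 0.05. It is 99.9%, so the stated power above 90% reproduces.

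**Effect on the difference.** Each control moved to responder lowers it by 1/51 = 1.96 points; three lower it by 3/51 = 5.9 points. For 5/12 treated responders (41.7%):
- against 7/51: 41.7 − 13.7 = 27.9 points (from unrounded values)
- against 8/51: 26.0 points
- against 10/51: 22.1 points

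**Effect on the significance bar.** Smallest treated count out of 12 with p ≤ 0.05:

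| Controls /51 | Rate | Treated needed | p there | p one lower, where computed |
|---|---|---|---|---|
| 3 | 5.9% | 4 | 0.0205 | |
| 4 | 7.8% | 4 | 0.0365 | |
| 5 | 9.8% | 5 | 0.0165 | |
| 6 | 11.8% | 5 | 0.0270 | |
| 7 | 13.7% | 5 | 0.0413 | 0.1974 (4/12) |
| 8 | 15.7% | 6 | 0.0184 | 0.1054 (5/12) |
| 9 | 17.6% | 6 | 0.0276 | |
| 10 | 19.6% | 7 | 0.0116 | 0.0593 (6/12) |

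Reading down from the starting count:
- From 7/51, one reclassification moves the bar from 5 to 6 and three move it to 7.
- From 5/51, one or two leave it at 5 and three move it to 6.
- From 3/51, one leaves it at 4 and two move it to 5.

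**How robust a given result is.** Largest control count at which significance survives:
- 5/12: 7/51
- 6/12: 9/51
- 7/12: 13/51
- 8/12: 17/51
- 10/12 (about the expected 85%): 24/51 (p=0.028; at 25/51, p=0.051)

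**Power.** At 85% response, with the control count varying binomially, power is 99.9% at a control rate of 7/51 and 90.6% at 17/51. At an assumed 50% response it is 71.2% at 7/51, 64.3% at 8/51 and 50.4% at 10/51.

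**Can trial data test the assumption?** Children dosed under 24 months start HFMSE on reaching 24 months (Protocol 11.1.1). With the SAP's 30-day month, that falls (24 − age at dosing) × 30 days after dosing: about day 360 if dosed at 12 months, day 180 at 18 months, and day 450 at 9 months, which is after Month 12. Children dosed from about 12 months of age can therefore have both scales within follow-up.

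**The case against.** The strongest reply is that the gap is narrow even on its own premise. The rules differ only for a control whose best stand at any visit within 12 months ends at about a count of 3. The premise is also unproven: if counts run faster than seconds, score 2 could be as easy as Bayley #40 or easier, and counting scores of 1 or 2 would then over-credit controls. Both points stand. They are why the effect may be zero and why the proposed analysis is a bound, not a corrected estimate.

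Other differences run both ways. Against AVXS-101, controls already standing at Baseline count as responders. No non-standing criterion is listed for the 51 controls, while Protocol 8.2 excludes any child who has ever stood. The *SMN2* modifier was not assessed in PNCR, and treated milestones need central video confirmation. In its favour, treated children are assessed monthly and family videos count, whereas for PNCR "Study visits were scheduled at baseline and at 2, 4, 6, 9, and 12 months and every 6 months thereafter". Net bias is therefore not established. That does not remove the value of sizing this element, since the plan lets the reader see none of them.

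The 5/12 against 7/51 example is also an edge case. SAP 19.3 suggests that control milestones could count at any time; if 7/51 is such a count, the 12-month figure is at most 7. For starting counts of 3 to 7, one reclassification moves the bar only from 4 or from 7.

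Finally, PNCR data already exist, so power could be computed with the control count fixed. That gives 99.99% at 7/51 and 97.6% at 17/51 for 85% response, and 80.6%, 61.3% and 38.7% at 7, 8 and 10 of 51 for 50% response. Either model leaves the stated power intact. The bodies of SAP 4.3 and 8.3 are not visible, but the 8.3 titles in the contents list concern Bayley and HFMSE score changes, not item 19.

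**Conclusion.** The concern holds as a conditional one. If a count of 3 is about 3 seconds, the control threshold is stricter, and this element alone can only favour AVXS-101 or have no effect. The size is unknown and possibly zero, at 2.0 percentage points per reclassified control. The power claim is safe, and a result near 10/12 would survive up to 24/51 controls. The significance conclusion could change only for a result close to the boundary, such as 5/12 against 7/51. No claim is made about net bias across all the differing rules. It should be fixed because it affects the primary comparison and is cheap to resolve. Confidence is medium, because the count-to-seconds link and the score-1 count are both missing.

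**What to change.** Keep score 2 as the primary control definition, because SAP 2.2.2 says an efficacy analysis was already conducted when Cohort 2 completed Month 12.

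- In SAP 8.1.1, add one reported sensitivity analysis, labelled as added after that analysis. It defines control standing as item 19 score 1 or 2, for the Fisher test, the difference with its exact 95% CI, and the Cox model.
- Report PNCR counts by best item 19 score (0, 1, 2) within 12 months of Baseline. In SAP 5.6.1, give the control rate under both definitions beside the 14%. Leave the planning assumption in SAP 3.7 unchanged.
- For Dose B children in this age group with HFMSE in follow-up, tabulate item 19 score against whether Bayley #40 had been attained by that visit. This checks the count-versus-seconds assumption descriptively. It will miss children dosed before about 12 months of age, whose number is not given.

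The cost is a short SAP addition and a few re-runs on PNCR item scores and trial HFMSE data already held. The control rate may rise, making the comparison look less favourable, and the analysis will be post hoc. If no control has a best score of 1, the question is closed.

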### **5.6.2. Sensitivity analyses vs. PNCR**

The primary PNCR group consists of 15 patients to be used for the analysis of efficacy in the older cohort patients, but one patient included in the cohort had an HFMSE score of 0 recorded at Baseline and all post-Baseline visits. Additionally, data collected more than 12 months after the Baseline assessment has occurred were being considered. The PNCR database was re-reviewed in order to identify a secondary PNCR population upon which to compare to AVXS-101 via sensitivity analyses. The secondary PNCR population consisting of 17 patients was identified as follows:

The PNCR database was filtered to identify individuals who matched eligibility criteria for CL-102 as closely as possible. Seventeen individuals were identified with age, clinical, and genetic criteria that were similar to CL-102 study patients. HFMSE scores were used to determine natural history of disease progression. The PNCR controls were 2-5 years of age. The first visit within the 2 to 5 year interval was defined as the baseline visit. Subsequent visits within a 12 month interval were used to determine change from baseline for HFMSE. Clinically, these individuals were able to sit without support but did not stand or walk. Genetically, patients harbored biallelic SMN1 deletions and 3 copies of SMN2. Not all patients in this group had a full 12 months of follow up data. Hence, this group underestimates decline during a 12 month period.

From this point forward, this PNCR comparator group of 17 patients will be referred to as the “Sensitivity PNCR” group.

### **5.7. Pharmacokinetic Set**

Not applicable for this SAP.

